Other Important Variables: Age, race, ethnicity, gender, sex at birth, and CJI history; as well as COVID-19 knowledge, testing history, infection history, substance use history, beliefs around mask efficacy, treatment/prevention history, vaccine knowledge/attitudes, prior contact by contact tracer, experiences of racism, housing status, food insecurity, employment, experience of violence, workplace resources, PPE availability, and known COVID-19 contact.

Analytic overview. Two types of analyses will be performed.

The first will focus on the likelihood that a participant's network members are referred for testing. This will be modeled using logistic regression, with each network member treated as an observation (tested versus not). A three-level hierarchical model will be used, with random effects at the level of the study participant (level two) and the recruitment cluster (level three, all participants referred by the same index participant).⁴³ We shall also consider adding site as a fourth level to permit us to estimate between-site variability both in the outcomes and in the effectiveness of the interventions.

The second analysis will focus on the total number of individuals referred by a participant for testing, including both network members and additional referrals not initially named as part of the participant's network. The total number of referrals will be modeled using negative binomial regression.⁴⁴ A random effect at the level of the recruitment cluster will again be included to capture potential within-cluster correlation in the number of referrals. To ensure correct inferences even in cases where our models do not fully capture the within-cluster correlation in the data, we shall use the clustered version of the robust (i.e., sandwich) variance estimator throughout.⁴⁵

Primary outcome analysis (overall comparison of SNS vs. SNS + messaging). The primary outcome analysis will compare the likelihood of testing among network members and the total number of referrals tested between those assigned to SNS and those assigned to SNS plus messaging. Our initial analysis will not adjust for covariates, relying instead on the randomization to justify the comparison. We shall then incorporate covariates—measured at both the level of the network member (e.g., member characteristics and the nature of the relationship to the participant) and of the participant—to improve the precision of our estimates and to identify demographic and social characteristics associated with differences in referral yield. In addition, we shall consider interactions between intervention group (SNS vs. SNS + messaging) and participant characteristics to determine whether messaging is more effective in certain groups than others. Since we shall consider several possible interactions, we shall use partial pooling within a Bayesian estimation framework⁴⁶ to avoid bias and address the issue of multiple comparisons.

We will compare the probability of participants being vaccinated in the SNS vs. SNS + messaging arm using logistic regression with each participant treated as an observation (vaccinated vs. not). This will be modeled with a three-level hierarchical model with random effects at the level of the recruitment cluster and study site. We will also consider adjustments for time trends in vaccine availability and participant eligibility.

Secondary outcome analyses: We shall use negative binomial regression to compare the average number of referrals tested per index client between those recruited to C3 and assigned to the SNS condition and a comparison group of clients at the same sites receiving standard contact tracing only. This analysis will be performed first using only those contact tracing clients who visited the sites on a day randomized to no C3 recruitment, since these individuals should, on average, be similar to those recruited into the study. A subsequent analysis will be performed using a larger set of non-study clients to increase precision; this will use covariates capturing demographic and other client characteristics to adjust for potential differences between the C3 SNS group and the non-study comparison group. Analyses will use generalized linear mixed models similar to those described above, as appropriate.

Power calculations: In order to estimate our power, we performed the following simulation. We assumed that index participants generate network members according to a negative binomial distribution with mean 4 and SD 2.8 (to match the study design, networks larger than 6 were truncated). Each network member comes in for testing with a probability determined by the group to which they are assigned, and we conservatively assume intraclass correlations of 0.46 within a participant's network and 0.37 within a recruitment cluster. If we assume that the overall likelihood of testing among network members is 0.44 among the SNS group and 0.52 among the SNS plus messaging group, then an overall sample size of 2,400 participants will provide approximately 87% power to detect the difference at the 0.05 level (twosided). We shall have approximately 80% power to detect an interaction between the intervention and a binary participant characteristic (Groups A and B) such that the overall probability of testing for those receiving SNS only (both A and B) is 0.44, the probability of testing for those in Group A receiving SNS plus messaging is 0.50, and the probability of testing for those in Group B receiving SNS plus messaging is 0.63 (i.e., messaging is more effective among Group B).

Attrition and missing data: All participants enrolled in the study will be included in our analyses; since the primary outcomes will be measured based on referrals coming in to get tested which does not require additional participation by the participant, we anticipate very little missing outcome data (referrals who come in for testing and decline to identify the person who referred them will not be counted). Any missing data will be addressed using multiple imputation⁴⁷ or by using a fully Bayesian approach to estimate the model⁴⁸ (in which missing data are essentially treated as additional unknown parameters).

POTENTIAL RISKS AND BENEFITS TO SUBJECTS

Study Risks. Interviewed subjects will be exposed to minimal risk: loss of confidentiality and discomfort from the questionnaire. Subjects will be told they do not need to answer any questions that make them uncomfortable. Linkages between study participants are collected through a code/code word process that our team has used in previous network referral studies. All survey data will be collected using a tablet and linked through the subject's study code instead of name. Tablets will be encrypted and data will be password-protected and HIPAA compliant. At all sites, COVID infection control procedures will be in place. These will include a COVID symptom screener (Appendix F), temperature checks, mask-wearing requirement and at least six feet apart during in-person interactions.

Benefits: The primary potential benefits of this research will accrue to participants of this study and their networks. Participants will be linked to COVID-19 testing and treatment services as needed. The results of this study may lead to future interventions which can support COVID-19 prevention messaging, linkage to testing and treatment services for disenfranchised populations.

DATA STORAGE AND SHARING

We shall take several steps to ensure the security of the identifiers and data collected for this study. First, all data will be collected using dedicated laptops purchased by the project and configured and certified by BSDIS to meet their requirements for portable computers (e.g., timed log-out, whole-disk encryption, use of BigFix and antivirus software, etc.). Data will be entered into two applications: REDCap (web-based application hosted by the CRI at the University of Chicago) and Network Canvas (developed at Northwestern University, and running locally on the laptop). The social network data, including identifiers for social network members, will be entered into Network Canvas, which has been specially designed for collection of such data. Following an interview, the data will be exported from Network Canvas and the network member identifiers will be split off and placed in a separate file which will then be strongly encrypted using RSA via the software GnuPG (an implementation of the OpenPGP standard as defined by RFC4880). This operation will be performed programmatically, using a custom utility installed on the laptop. After verification of the encrypted file, the unencrypted file will be deleted.

Before any data transfer, the University of Chicago will encrypt the data both at rest and in transit via a Shared File Transfer protocol (SFTP) to provide a high level of security of sending and receiving file transfers. The encrypted data products will be securely uploaded to a SFTP server using a cyberinfrastructure service such as Globus (<https://www.globus.org/>) via the Biological Science Division Information Services (BSDIS). Using a SFTP will ensure high security features that meet authentication and authorization standards for sensitive data containing protected health information. Additionally, data management and transferring services for personally identifiable data will be with a High Assurance or HIPAA BAA subscription. If an institution is responsible to provide data (incoming), they will be responsible for encryption. Thus, the network member identifiers will be encrypted both *in transit* and *at rest*.

The identifiers of network members will be firewalled from all other data in two ways. First, they will be uploaded and stored in a separate, dedicated fileshare. Second and more importantly, an honest broker within the University of Chicago Biostatistics Laboratory will hold the encryption key for the identifiers. Only this individual will be able to decrypt the files containing the identifiers (i.e., our protocol achieves end-to-end encryption between the laptop in the field and the honest broker). He or she will monitor the incoming files to ensure that the system is working properly, but the files will continue to be stored in encrypted format. The honest broker will not be a member of the research team, and will not have access to any of the other data collected by the project.

Finally, the honest broker will provide study subject and network member location identifiers to one or more data analysts who will perform the network matching and geocoding needed to generate files for analysis. This analyst (or analysts) will be located at the University of Chicago (e.g., CCHE, the Biostatistics Lab, the Center for Spatial Data Science, or Argonne), and his or her only role on the project will be to perform the network matching and geocoding. Once this operation has been completed and the results have undergone QC, the original files containing network member identifiers will be destroyed by both the analyst(s) and the honest broker. All network matching and geocoding will take place on a secure compute server maintained by the Research Computing Group in the Department of Public Health Sciences. This is the only location where the raw files will be decrypted.

After study termination, the de-identified study data may be maintained for up to 10 years at the University of Chicago. All recordings of study trainings will be destroyed upon study termination.

UAMS will destroy any raw data received from Arkansas Department of Health upon study completion.

The Duke Clinical Research Institute (DCRI) has been chosen by the National Institute of Health (NIH) to serve as the data coordinating center for all of the RADx-UP study centers. Coded data for all sites participating in our RADx-UP C3 study will flow from University of Chicago to DCRI for storage and sharing

purposes for future COVID 19 research as directed by the NIH (in keeping with the NIH's policy). All data shared in this manner would be deidentified and could be used indefinitely.

REFERENCES

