- 1) Visually display a driver's license or state ID

- 2) Visually display an alternative photo ID (employee ID, school ID, etc) in combination with a piece of mail displaying the subject's name.
- 3) Visually display an alternative photo ID (employee ID, school ID, etc) alone
- 4) Visually display one of the following pieces of mail with subject's name and address: utility bill, cellphone bill, correspondence from the secretary of state or other government organization
- 5) Visually displaying any piece of mail listing the subject's name and address
- 6) Asking the subject to verbally state their name

2. **Day 1 Survey.** Following consent, study participants will complete an electronic survey that includes social network inventory. Identifying information of social network members (first name and last initial and cross streets/zipcode/neighborhood) is collected through self-report for the purposes of connecting social networks of study subjects. Day 1 Survey is found in Appendix B. This will survey will be completed on the day of recruitment and will take 60 minutes. The RA can interview participants who have difficulty self-administering the survey.
3. **Randomization.** Will occur following the survey, and participants in the SNS+messaging arm will receive the messaging intervention (discussion tools and coaching). Study participants will be randomized to receive no messaging (i.e., SNS only) or SNS+messaging with equal probability. Randomization will be performed at the participant level, meaning that in general, participants within a recruitment cluster will be assigned to different groups. Random assignments will be provided by the University of Chicago via a web-based API, with the touchpads programmed to retrieve an assignment at the appropriate time and deliver the messaging (or not), as appropriate.

Indexes and first-degree referrals will be randomized as described above. Second-degree referrals will also be randomized, however, we will not ask for additional SNS referrals from them if the study sample size has been reached.

4. **Messaging Intervention.** Study staff will be notified of group allocation and provide the in-person message reinforcement and will address questions related to messaging.

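### The count primary outcome is first compared unadjusted, and the later adjusted analysis neither names Day 1 network size nor is ranked; pre-specifying that covariate would give a useful, free gain in precision.

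*Combined protocol and SAP*

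**What the plan says.** The count is the first item under Primary Outcomes. The Analytic overview gives its model: "The total number of referrals will be modeled using negative binomial regression". On clustering it adds: "A random effect at the level of the recruitment cluster will again be included", with a cluster-robust variance throughout. The count is wider than the named network, "including both network members and additional referrals not initially named as part of" that network.

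The Primary outcome analysis section begins unadjusted: "Our initial analysis will not adjust for covariates, relying instead on the randomization to justify the comparison". It then adds member-level and participant-level covariates "to improve the precision of our estimates and to identify demographic and social characteristics associated with differences in referral yield". The examples given are at member level only. The participant-level set is left open, and nothing says which of the two analyses decides the outcome.

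Under Study Visit Procedures, item 2 (Day 1 Survey), "study participants will complete an electronic survey that includes social network inventory". Item 3 (Randomization) says of its own timing: "Will occur following the survey". The size of the inventory is therefore a baseline variable. It is not in the list headed Other Important Variables. The hypothesis paragraph under Methods names network composition only as a possible source of differing effects.

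The Power calculations section generates networks "according to a negative binomial distribution with mean 4 and SD 2.8", truncated at six. It states power for the proportion of network members tested and none for the count.

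**The concern.** How many people a participant brings in depends partly on how many they have to ask, and the plan's own power inputs make that number very variable. An unadjusted comparison leaves all of this variation in the error term. With a moderate number of referring participants, a real messaging effect on a primary outcome could be missed although the data needed to sharpen the comparison are already held.

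The planned second step does not settle this. It accepts adjustment for precision in principle but does not commit to the strongest baseline predictor that the plan's inputs imply. A covariate chosen after the data are seen carries less weight than one named in advance, and two unranked results leave open which one counts.

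**Working it through.** **Inputs** (Power calculations): network size M negative binomial, mean 4, SD 2.8, truncated at six; intraclass correlations 0.46 within a participant's network and 0.37 within a recruitment cluster; testing probabilities 0.44 and 0.52; 2,400 participants; 1:1 allocation (Randomization).

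**The plan's stated power.** The figure of about 87% is for the proportion outcome. The structure of that simulation is not fully stated, and I could not reproduce it without adding assumptions. If all 2,400 refer, power is 99% or more. If only index and first-degree participants refer, most variants give 80-85%, and nested correlations with full weighting give 98%. I do not call the figure wrong, and the variance shares below do not depend on it.

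**Network size.** Variance 2.8² = 7.84, so the dispersion parameter is 16/(7.84 − 4) = 4.17. Capped at six: E(M) = 3.53, Var(M) = 3.77, E[M(M−1)] = 12.72. About 6% of networks have size zero.

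**Variance of the count Y, by the law of total variance**

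- Explained by M: p² Var(M)
- Not explained: p(1−p) × {E(M) + 0.46 E[M(M−1)]}
- Cluster component within the unexplained part: 0.37 p(1−p) [E(M)]²

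| | p = 0.44 | p = 0.52 |
|---|---|---|
| Explained by M | 0.1936 × 3.77 = 0.73 | 0.2704 × 3.77 = 1.02 |
| Not explained | 0.2464 × 9.39 = 2.31 | 0.2496 × 9.39 = 2.34 |
| Total | 3.04 | 3.36 |
| Share of total | 24% | 30% |
| Cluster component | 1.14 | 1.15 |
| Share after removing it | 0.73/1.90 = 38% | 1.02/2.21 = 46% |

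Here 9.39 = 3.53 + 0.46 × 12.72. If truncation instead means conditioning on six or fewer, the shares are 25-31% and 38-46%. If unnamed referrals unrelated to M add 10-25% to the count (an assumption), the capped shares fall to 21-29% and 32-43%.

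**Effect on the treatment comparison** (simulation, with and without M)

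| Model | SE without M | SE with M | Cut in variance |
|---|---|---|---|
| Marginal log-link, cluster-robust, all 2,400 refer (log rate ratio) | 0.0436 | 0.0375 | 1 − (0.0375/0.0436)² = 26% |
| Within-cluster least squares, all 2,400 refer (mean difference) | 0.0630 | 0.0480 | 42% |
| Exchangeable, 1,155 refer (log rate ratio) | 0.057 | 0.041 | 48% |
| Exchangeable, 960 refer (log rate ratio) | 0.062 | 0.043 | 52% |

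The within-cluster and exchangeable models stand in for the planned cluster random effect. None of these is the planned model itself.

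**How many refer.** The plan does not fix this. Second-degree participants need not be asked for referrals once the sample size is reached. If 300 indexes produce 2,400 over three waves, 300(1 + r + r²) = 2,400 gives r = 2.19, so index plus first-degree participants number about 300 × 3.19 = 957. The higher value of 1,155 is roughly where the stated inputs give 87% for the proportion under one set of assumptions. Both are inferred.

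**Power for the count**

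- About 900 refer: 63% to 76% (marginal), 68% to 89% (within cluster), 74% to 97% (exchangeable).
- 1,155 refer: 83% to 98% (exchangeable). Repeat runs differ by a few points, so I take the overall range as 63-86% rising to 76-99%.
- All 2,400 refer: 98% to 99.7% (marginal), 99.7% to 100% (within cluster).

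**The case against.** The strongest reply has four parts.

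*The plan already adjusts for precision.* This stands. A reader might infer that the plan ignores covariates or rules network size out. It does neither: the adjusted step is there and its participant-level list is open. What is missing is the named covariate and the ranking.

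*The tested proportion is also primary and takes each network member as an observation.* This largely handles network size for that outcome. It does not help the count, which is listed separately and includes people outside the named network.

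*The numbers rest on equating two quantities.* The simulated network is truncated at six to match the study design, and six is also the cap on paid referrals. It may describe people who can be referred and not the length of the Day 1 inventory, for which the text gives no distribution. For illustration, if the two correlate at 0.5 to 0.7 (an assumption), a 27% share falls to r² × 27%, about 7-13%. The background's appeal to homophily also makes it plausible that size is alike within a recruitment cluster, in which case the planned random effect already absorbs part of it. Both points stand and limit confidence in the size of the gain.

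*The unadjusted randomised comparison is legitimate.* This also stands. A reader might infer bias or an invalid test. Nothing in the documents supports that: network size is balanced by randomisation in expectation, and the variance estimator is cluster-robust.

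**Conclusion.** The point holds as one of efficiency and pre-specification on a primary outcome. The initial count comparison omits a strong predictor known before randomisation, and the later adjusted analysis neither names it nor is ranked.

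It would be tempting to say that a third to a half of the count's variance is left in needlessly. The inputs do not support that for total variance, where the share is about a quarter to 30%. Only the variance left after the cluster component gives 38-46%. Most of the total (about 70-76%) comes from clustering and from chance in who is tested.

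The cut in the variance of the treatment effect, about 26% to 40-50% by model, is better supported than the power gain, which depends on the inferred number of referrers and nearly vanishes if all 2,400 refer. All figures assume that simulated network size represents the Day 1 count and is independent within recruitment clusters. If either fails, the gain is smaller.

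**What to change.** Pre-specify as the headline count analysis the negative binomial model with arm, Day 1 network size and the recruitment-cluster effect, with the planned robust standard errors. State that the unadjusted model is a sensitivity analysis.

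- Fix the functional form in advance. One example is log(size + 0.5), which copes with networks of size zero.
- Enter size as a covariate and not as an offset, because the count includes people not named at Day 1.
- Use only the Day 1 inventory. The Day 21 inventory is taken after randomisation and could be affected by the messaging.

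The cost is one sentence in the analysis plan, settled before outcome data are examined by arm. No new data and no extra participants are needed.
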